Eligible children and their families will be recruited to include preschool children 1.5-4.5 years (18 to 54 months) at the age of enrolment, who are not expected to enter school/kindergarten within 6 months of enrolment. Children will be living in four diverse parts of Canada to ensure national representation and future scalability: British Columbia, Manitoba, Nova Scotia, Quebec. Participants' postal codes will be analyzed to ensure representation: rural/remote, small urban and large urban/metro representation with purposeful sampling as required. From the patient population perspective, two different groups that are likely to manifest new global developmental delays at this stage will be recruited. They are at high risk for brain-based developmental delays, however some will have no delay and others will have mild, moderate or severe delays.

Children at risk who are not yet receiving developmental services: Primary care provider and/or parental concerns regarding their child's developmental progress become apparent in the preschool years.

Inconsistent use of screening tools and variation in triage and assessment methods often result in delayed detection and long wait lists for services. Children will be those waiting for their first formal appointment for diagnosis and assessment for “developmental delay”, from a public health facility, a child developmental centre and/or a dedicated hospital clinic. These children represent a group who are not currently receiving developmental services. These children may be found to have no delay, a delay in one domain (e.g. specific language impairment) or global delays, which can be mild to severe. This will be a consecutive sample on the wait list and who are between 1.5-4.5 years of age.

For this trial, children/families will be excluded if they: (1) are non-English speaking (and non-French speaking in sites where services are available in French); (2) are unwilling or unable to meet with the study team for intermittent assessments; (3) do not have access on a routine basis to the internet through a desktop or mobile device. We will recruit 350 subjects, 175 for both intervention and control arms.

Study procedures: Intervention and control

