Recruitment will begin with family contact. Each site manages their own recruitment process and protocol. Please see our *Recruitment Protocol* in Montreal (Appendix). Families will be contacted via the centre to which they were referred for developmental diagnosis and assessment. A member of the clinical team will ask if they are interested to learn more about the BRIGHT Coaching study. If interested, the families' contact information will be shared with the local research assistant (RA) overseeing the trial. The RA will speak to a parent by phone and follow up with an introductory letter by mail and/or email explaining the procedures of the study, together with the consent form. After 1 to 10 days, the RA will call the family to determine interest in participating and answer any questions. If interested in participating, parent can either 1) sign the consent form and scan by email to the RA, 2) send the consent form to the RA by mail/ hand it to them in person, 3) agree to a verbal consent process and verbal consent will be given to the RA over the phone (in accordance with the Tri-Council Policy Statement on verbal consent). Once consent is signed, participants will conduct baseline assessments including documentation of their care and social networks, and be randomized using a computer-generated algorithm; randomization will be stratified by site. The allocation ratio for intervention or control will be 1:1 for each site.

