Descriptive statistics will be used to characterize our sample in the experimental and control arms. The primary analysis is to ascertain benefit of the BRIGHT system (Coach + online education tools + online peer support) compared to usual care (control) will be between group (intervention vs control) comparison of primary and secondary outcomes using t tests (two-sided, $p<.05$). Statistical comparisons will be made at 8- and 12- months post enrolment, to determine if group differences manifest early and if they continue to improve or stabilize. This will be important in determining whether the BRIGHT system is necessary over a prolonged period (8 vs 12 months) to achieve its goals. Principles of intent-to-treat analysis will be applied. Repeated measures with mixed model analysis will be used to assess effect of group category and province with intervention at two time points. Within the intervention group, predictors of change scores between baseline and outcomes (dependent variable) will be tested to determine which children/families are more likely to be responsive to the BRIGHT system. Multivariate linear regressions will be conducted with independent variables, to include: parent readiness score, sociodemographic factors, child's functioning (Vineland), province, and engagement in the Igloo platform. The structural properties of the network (Igloo) will be analysed using UCINET [17]. Network analysis related to patterns of use of the online platform will be correlated with the outcome measures of interest in this study.

Sample size:

We will recruit 392 participants; we project a sample size of 352 based on: i) two-sided test of the null hypothesis at $\alpha=.05$, ii) $\beta=.80$, iii) 10% attrition; iv) difference of 0.3 SD.

Studies as of yet have not identified a minimal clinically important difference (MCID) for our primary outcome measure (the Family Empowerment Scale) that could be used to estimate sample size calculation. In the absence of a “clinimetric” MCID, a distribution-based methods approach is commonly applied that proposes a fraction of the pooled Standard Deviation (i.e. utilize effect size estimates). In this case, the difference of 0.3 standard deviation can be used to detect modest effects that may be clinically significant; or 0.5 SD for moderate to large effects [18, 19].

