We aim to recruit a sample of 350 participants (randomized to either intervention or control group) across the four sites. This will be approximately 100 from British Columbia, 100 from Quebec, 75 from Manitoba and 75 from Nova Scotia. In order to be able to detect modest effects that may be clinically important (0.3 SD), this would require recruitment of a sample of 392, accounting for 10% attrition, for a sample of 352. Furthermore, this larger sample size would enable us to account for cluster randomization. We expect that all participants are independent, whether or not they live in any of the provinces. Nonetheless, it is conceivable that the association within provinces is slightly stronger (weak ICC=0.100) than the association between participants across provinces, due to environmental context (i.e. different health care and social service systems). A sample size of 346 (recruit 384, 10% attrition) would allow us to account for cluster randomization. We will apply a linear mixed model to account for the possible effect of province on the benefits of treatment on empowerment and parent competency.

PLANS FOR KNOWLEDGE TRANSLATION

The results of this study will be relevant to families, health service administrators, policy makers and providers.

Families: Families will be important consumers of the results of this study. In order to determine how best to communicate the results to them, a focus group of families will be brought together. They will guide strategy and tactics with respect to the study results. The content for this knowledge translation will be particularly focussed on the benefits and challenges from the perspective of families. With respect to tactics, it is anticipated that family councils, childhood-disability focussed organizations, the media, family-guided web-based materials and providers will be modalities undertaken to reach families. This plan will be modified subsequent to the focus group with families after the conclusion of the study.

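### The sample-size section claims to allow for cluster randomisation in an individually randomised trial, with a figure (346) that its ICC of 0.100 does not produce, and the protocol gives conflicting recruitment targets, one of which has about 76% power

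*Protocol*

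**What the plan says.** Four parts of the Protocol bear on this.

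- **Design.** Study procedures: Intervention and control has each consenting family complete baseline and then be randomised by computer: "randomization will be stratified by site. The allocation ratio for intervention or control will be 1:1 for each site".
- **Cluster wording.** Sample size says of the 392/352 option: "Furthermore, this larger sample size would enable us to account for cluster randomization". It then expects participants to be independent, but adds that "it is conceivable that the association within provinces is slightly stronger (weak ICC=0.100") than across provinces, and concludes: "A sample size of 346 (recruit 384, 10% attrition) would allow us to account for cluster randomization". It shows no formula, cluster size or design effect.
- **Recruitment target.** Participants: "We will recruit 350 subjects, 175 for both intervention and control arms". Sample size opens with "We will recruit 392 participants; we project a sample size of 352 based on" a two-sided 0.05 test, 80% power (printed as a beta of .80), 10% attrition and a difference of 0.3 SD. Later in the same section: "We aim to recruit a sample of 350 participants (randomized to either intervention or control group) across the four sites", with site targets of about 100, 100, 75 and 75. That paragraph then returns to 392 and adds 384.
- **Analysis.** Statistical analyses makes the primary analysis a between-group "comparison of primary and secondary outcomes using t tests", with a mixed model including province besides. The end of Sample size assigns the effect of province on treatment benefit to a linear mixed model.

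**The concern.** The unit of randomisation decides how a sample size is calculated and analysed. If provinces were the randomised units, an ICC of 0.100 would inflate the sample size many times over. With families randomised within provinces, the same ICC describes outcome variance that stratification balances across the arms, and it reduces the number needed once site is in the model. The section uses the language of the first design for a trial of the second kind, and the number it gives belongs to neither at the stated ICC.

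The practical stake is the recruitment target. Three sizes stand side by side (392/352, 384/346 and 350), and a reader cannot tell which one carries the 80% power. Sites working to the listed targets would stop at 350, which is 392 − 350 = 42 families short of the number the power statement uses.

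**Working it through.** **Inputs** (all from the Protocol): difference 0.3 SD; two-sided alpha 0.05; power 0.80; attrition 10%; 1:1 within site; ICC 0.100; four provinces of about 100, 100, 75 and 75.

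**1. The plan's base figure.** Normal formula per arm: 2 × ((1.960 + 0.8416)/0.3)² = 174.42, so 175 per arm, 350 in total. The t-test version gives 175.4, so 176 per arm, 352 in total. Then 352/0.9 = 391.1, so 392. The 352/392 pair reproduces; exact t-test power at 352 is 80.1%.

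**2. 346 as a cluster-randomised size.** Design effect = 1 + (m − 1) × ICC. With m = 346/4 = 86.5 it is 1 + 85.5 × 0.100 = 9.55, and 350 × 9.55 ≈ 3,343 evaluable. The effective size of 346 would be 346/9.55 ≈ 36. With four clusters the effective size cannot exceed 4/0.100 = 40, so this design could not reach the target at all. An allowance of this kind cannot fall below the unadjusted 352.

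**3. 346 under the design described.** With families randomised within site and site in the model, residual variance is (1 − ICC).

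- Normal formula at ICC 0.100: 348.84 × 0.90 = 313.96, so 314.
- Noncentral t with N − 5 degrees of freedom: power 79.9% at 315 and 80.0% at 316, so 316 are needed.
- At 346, power is 83.5% at ICC 0.100 and 79.5% with no ICC credit.

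So 346 is not the size for ICC 0.100 here either.

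**4. Where 346 may come from.** At ICC 0.010 the normal formula gives 174.42 × 0.99 = 172.7, so 173 per arm and 346 in total. Then 346/0.9 = 384.4, printed as 384. The match is exact, but the Protocol shows no formula and prints 0.100.

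**5. The recruitment targets.** Site targets: 100 + 100 + 75 + 75 = 350. Evaluable after 10% attrition: 350 × 0.9 = 315.

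| Recruited | Evaluable | Power at 0.3 SD, no ICC credit |
|---|---|---|
| 392 | 352 | 80.1% |
| 384 | 346 | 79.5% |
| 350 | 315 | 75.6% |

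With 315 evaluable, 80% power is reached at a difference of 0.317 SD. With site in the model, power at 315 depends on an ICC that is itself in doubt: 76.0% at 0.010, 77.7% at 0.05, 79.9% at 0.100, 82.1% at 0.15.

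**6. The unadjusted t test.** With arms balanced within site and ICC 0.100, the true variance of the difference is 0.9 of what the test assumes. Type I error is 2 × P(Z > 1.96/√0.9) = 3.9% by normal approximation. A simulation with four provinces gave 4.2%. Simulated power at 352 was 81.6% unadjusted and 83.7% with site in the model (84.1% by the noncentral t).

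**The case against.** The strongest defence is that 346/384 was computed for the right design. A number slightly below the unadjusted one is what stratified individual randomisation produces, the text calls the ICC weak, and 346 matches ICC 0.010 exactly. On that reading the errors are the printed ICC and the word cluster, and the number is sound. This stands as a possibility, so the fix should not insist on deletion. It cannot be confirmed, and on the printed ICC the number is still unsupported.

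A second defence is that 350 means evaluable families, since the normal formula gives exactly 350. But both statements of 350 speak of recruiting, the site figures are recruitment targets, and Sample size itself contrasts 350 with the larger 392 that it says 0.3 SD requires.

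A third is that the Protocol already plans mixed models with province, and that the exact covariate set may be left to a statistical analysis plan. That is fair, and site adjustment of the primary comparison is therefore only optional here.

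Two stronger readings are tempting. One might infer from the cluster wording and ICC 0.100 that the trial is grossly underpowered and needs thousands of families. It does not: families are randomised individually within site, and a between-province ICC does not inflate the size. One might also infer that a t test ignoring province is invalid. It is not: with site-stratified allocation it errs on the conservative side, which costs some efficiency.

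**Conclusion.** The point holds as a matter of wrong and conflicting statements. The trial is not cluster randomised. The figure 346 does not follow from ICC 0.100 under either design (about 316, or more than 3,300). The recruitment target is given as 350, 384 and 392.

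The ICC error does no harm to power under the actual design: 346 evaluable gives at least 79.5%. The real loss comes with the 350 target, which after the Protocol's own 10% attrition gives about 76% power at 0.3 SD instead of 80%. This assumes that attrition is 10%, that 350 means recruited as written, and that no credit is taken for stratification. Claiming that 350 recruited still gives about 80% through site adjustment would rest on an ICC of about 0.100 or more, and the Protocol's own figures put that value in doubt.

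A reader might also take 346 to cover variation of the treatment effect between provinces. The Protocol does not say so: it assigns that to the mixed model and gives no variance for it.

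**What to change.** 1. In Sample size, replace both references to cluster randomisation with a statement that families are individually randomised 1:1, stratified by site.
2. Remove 346/384, or correct the ICC and state the formula that yields them.
3. Give one recruitment target in Participants and throughout Sample size, with its true power. For 392 recruited: 352 evaluable, 80% power at 0.3 SD; then correct both statements of 350 and the site targets. For 350 recruited: 315 evaluable, about 76% power at 0.3 SD (80% at 0.317 SD), with no reliance on an ICC.
4. Optional: include site, the stratification factor, in the primary between-group comparison. It uses 3 degrees of freedom and recovers some power if provinces differ.

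Items 1 and 2 cost only text, as does item 3 if 350 is kept. Choosing 392 means 42 more families than the present site targets, a number the Protocol already states; this point does not require that choice.

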Recently, a focus on care coordination (e.g. care planning, navigating healthcare system) has emerged in the literature for those with chronic disease [6]. At the same time, science has emerged demonstrating how patient education programs that promote self-management for those with specific chronic conditions have positive effects on health behaviours, improved health status, and decreased health care costs [7]. Health coaching research to date has, for the most part, focussed on improving motivation and adherence to health behaviours and to support lifestyle change in order to prevent the negative course of a disease [8]. Health coaching is tailored to the patients' knowledge needs, and can be delivered through many means – one to one or via telephone or technology [9].

The preschool years are a time of stress for families as their preschool child awaits assessment, or even as they receive services for brain-based disorders. Similarly, the system and society struggle to meet needs of families in a timely and appropriate manner in the face of escalating costs. Given these struggles, there is need to examine whether a health-coach style of intervention coupled with parent education delivered through an online platform can be effective in empowering families, by delivering information, providing social (parent to parent) supports, and decreasing demand on health and developmental services. This innovation provides a significant service re-design in a system at critical point of transition.

AIMS AND HYPOTHESES

Primary Hypotheses:

- (1) A standardized approach to “developmental coaching” (i.e. coach + online education tools + peer support network) is *feasible* in the real-life context and *acceptable* to mothers and fathers and can be delivered across multiple inter-provincial sites that recruit patients from urban/suburban/rural settings.
- (2) A standardized approach to “developmental coaching” enhances *parental health* (parents' empowerment and sense of competence, quality of life, and minimizes parenting stress), *family health care experience* (care coordination experience and process of care) at similar *health care cost* (economic analysis), when compared to usual care.

Secondary Hypotheses:

- (3) Given the differences that exist in caregiver burden, Fathers will contact the coach and use the online platform less frequently than mothers. (*sex/gender hypothesis*)

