IMPLICATIONS FOR CHILD AND FAMILY WELL BEING - PRACTICE AND POLICY

The preschool years between 3 and 6 years of age are a time of great developmental change and a time of great concern for parents who see differences in their child’s development. Coordination of services, for those children receiving them can be challenging and confusing. Waiting for services for those not yet

receiving them can lead to frustration and fear. From a policy and health/social system administrator perspective, despite large investments, waiting lists often exist.

At the conclusion of this study, should the hypotheses be proven to be correct, the following impact will be seen for the following groups:

- *Families:* This study will produce an evidence-based mechanism to support families during times of uncertainty. It will be effective across developmental severity levels making it very generalizable. It will enable families in feeling supported, will enhance family empowerment, will support enhanced family well-being. With guidance regarding services, it is expected that there will be reduced travel time and time off work for families, thereby reducing costs to families.
- *Policy makers and health administrators:* The results and KT products will provide mechanisms to facilitate discussion regarding how the program is delivered regionally. It is anticipated that the program and its key ingredients could be delivered through multiple means, allowing governments to tailor its use to reflect their provincial, regional and local nuances.
- *Service Delivery/Developmental Programs:* The draw on services across provinces will be reduced as families receive information that prevents them from being in the incorrect queue for services and assists them in coordinating their own services as has been done with other self-management programs in adults with chronic disease. Rural and remote service delivery will be enhanced through this care, which can be delivered from a distance.

TABLE 1. MILESTONES, DELIVERABLES

Major Project Activities/ Milestones	Year 1 (M)ilestones	Year 2 (M)ilestones	Year 3 (M)ilestones/ (D)eliverable	Year 4 (M)ilestones/ (D)eliverable	Year 5 (M)ilestones/ (D)eliverable
Clinical study protocol and ethics review	(D) Protocol finalized with family input (D) Ethics approves finalized protocol across sites				

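### The protocol says BRIGHT will be effective across severity levels if its hypotheses hold, but no hypothesis concerns severity and the only responder analysis using the Vineland has no control arm

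*Protocol*

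**What the plan says.** In the section on implications for practice and policy, the protocol lists expected impacts, introduced by "should the hypotheses be proven to be correct, the following impact will be seen". The entry for families contains "It will be effective across developmental severity levels making it very generalizable".

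The parts of the protocol that bear on this are:

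- **Aims and Hypotheses.** There are five hypotheses: feasibility and acceptability; parental health, care experience and cost against usual care; fathers' use of the coach and platform compared with mothers'; timing of platform use; and change in families' networks. None refers to the child's severity.
- **Participants.** The children span the full range: "some will have no delay and others will have mild, moderate or severe delays".
- **Statistical analyses.** The primary analysis is an overall two-sided t test between arms. In addition, "Repeated measures with mixed model analysis will be used to assess effect of group category and province with intervention at two time points". Severity is not named in either.
- **Statistical analyses, responders.** "Within the intervention group, predictors of change scores between baseline and outcomes (dependent variable) will be tested", with the Vineland among the predictors. The stated purpose is to learn which children and families respond better.
- **Baseline data collection.** The Vineland is taken at recruitment in all participants, so in both arms.

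**The concern.** An overall difference between arms estimates the average effect in the severity mix that was enrolled. It does not show that the effect is present at each level of severity. The sentence nevertheless makes effectiveness across severity levels, and hence wide generalisability, follow from hypotheses that are silent on severity.

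The analysis that looks as if it might supply the missing evidence cannot do so. Within the intervention arm, a relation between baseline Vineland and change in outcome mixes two things: how such families would have fared anyway, and how much BRIGHT added. Only a comparison with usual care at the same Vineland level separates them.

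The protocol plans a policy paper and briefing notes for ministries and materials for families. A severity claim carried into these could present BRIGHT as useful to a group of families in whom the trial had not shown any benefit.

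**Working it through.** **1. The plan's own figure.** Inputs from Sample size: difference 0.3 SD, two-sided 0.05, power 0.80 (printed as beta), 10% attrition; 1:1 allocation from Study procedures. The t-test formula gives 175.4, so 176 per arm, 352 in all; 352/0.9 = 391.1, so 392 recruited. The stated 352 and 392 reproduce, for the overall comparison only.

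**2. Overall result when one severity group gains nothing.** The protocol gives no severity shares or subgroup effects, so these are assumed. Let a share *s* gain zero and the rest gain *d* (in SD). The average effect is m = (1 - s)d and, with 176 per arm and SD 1, power is about Φ(m√(176/2) - 1.96) = Φ(9.381m - 1.96).

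| Share with no gain | Gain in the rest | Average effect | Overall test significant |
|---|---|---|---|
| 1/4 | 0.30 | 0.225 | 56% |
| 1/4 | 0.45 | 0.3375 | 89% |
| 1/4 | 0.50 | 0.375 | 94% |
| 1/3 | 0.30 | 0.200 | 47% |
| 1/3 | 0.45 | 0.300 | 80% |
| 1/3 | 0.50 | 0.333 | 88% |

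Unequal benefit adds a little spread in the intervention arm. Simulating it (20,000 trials per row) gives, in the same order, 56%, 88%, 93%, 46%, 79% and 86%. Taking both methods together, the ranges are 46-56% when the rest gain 0.3 SD and 79-94% when they gain 0.45-0.5 SD.

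**3. What the intervention-arm regression can show.** If the slope of outcome on Vineland is b1 under BRIGHT and b0 under usual care, the change in treatment effect per unit of Vineland is b1 - b0. The planned regression estimates b1 alone. Simulation of 1,500 trials per setting, 176 per arm, standardised Vineland, residual SD 1, overall effect 0.3:

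| True slopes | Intervention-arm slope significant | Two-arm interaction significant |
|---|---|---|
| 0.3 in both arms (no effect modification) | 98% | 5% |
| -0.3 under usual care, 0 under BRIGHT (real modification) | 5% | 79% |

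In the first setting the planned regression nearly always points to a responder group that does not exist. In the second it misses a real one.

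**4. Precision of a two-arm severity comparison.** For two severity groups of sizes N1 and N2, each split 1:1, the SE of the difference in effects is √(4/N1 + 4/N2).

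- Half and half (176 and 176): SE 0.213, 95% half-width 0.42 SD, power 65% for a 0.5 SD difference and 29% for 0.3 SD.
- One third and two thirds (117.3 and 234.7): SE 0.226, half-width 0.44 SD, power 60% and 26%.
- One quarter and three quarters (88 and 264): SE 0.246, half-width 0.48 SD, power 53% and 23%.

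A non-significant interaction in a trial of this size is therefore no evidence that the effect is uniform.

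**The case against.** The sentence stands well after the statistical sections, in a list of hoped-for impacts such as less travel time and a smaller draw on services, several of which also go beyond the numbered hypotheses. It specifies no analysis. Analyses of effect modification are commonly left to the statistical analysis plan, which is not at hand. The protocol does intend to ask who responds, and since the Vineland is collected in both arms, a proper two-arm analysis stays open. The percentages depend on chosen subgroup effects: one third at zero and the rest at 0.45 SD averages exactly 0.3 SD, so its 80% is simply the design power again.

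Most of this stands, and it limits the point. A reader might infer that the protocol sets a rule by which any overall success will be reported as success at every severity level, beyond the reach of the data. The documents do not say that: no passage fixes how the trial report will reach a severity conclusion, and nothing stops the investigators from examining severity. Nor can it be held against the protocol that a severity-by-arm analysis is not described, since one may exist elsewhere.

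Two things remain, both stated in the protocol itself. The severity statement is conditioned on hypotheses that do not contain it. And the responder analysis that is described is restricted to one arm, which is the wrong comparison for its stated purpose.

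**Conclusion.** The point holds as a matter of an unsupported statement and an unsuitable responder analysis. Proof of the hypotheses would establish an average benefit over the enrolled mix, not a benefit at each severity level. Randomisation, data collection and the primary test are not affected.

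The size is conditional. An overall success while a quarter to a third of children gain nothing ranges from about an even chance (rest gain 0.3 SD) to likely (rest gain 0.45-0.5 SD). These figures assume 352 analysed, a common SD within groups, and severity shares and effects that the protocol does not give. They show that such a result is quite possible, not that it is expected. The objection to the intervention-arm regression needs no assumption about shares: without a control arm, treatment effect by severity cannot be estimated.

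**What to change.** 1. In the Implications section, limit the sentence to the average effect of BRIGHT in a sample of mixed developmental severity.
2. In Statistical analyses, assess responsiveness by severity with an arm-by-baseline-Vineland term in the two-arm mixed model already planned, instead of relying on the regression within the intervention group. That regression may stay as a description of change among families who received BRIGHT.
3. Report the BRIGHT minus usual care difference in the Family Empowerment Scale at low and high baseline Vineland, with 95% confidence intervals, labelled exploratory.
4. State that precision is low (half-width for the difference in effect about 0.42-0.44 SD for a half or one-third split, wider for a smaller group) and that a non-significant interaction does not show a uniform effect.

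A formal gate, such as requiring the lower confidence limit to exceed zero at both the 10th and 90th Vineland percentiles, is not recommended. With a truly uniform 0.3 SD effect, 352 analysed and a roughly normal Vineland, it would be passed in only about 13% of trials.

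The cost is a change of wording and one model term, using data already collected at baseline. The downside is a weaker claim of generalisability.
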